8.2. Safety Assessments

8.2.1. Adverse Events and Serious Adverse Events

8.2.1.1. Definitions

Adverse Event

An AE is any untoward medical occurrence in a clinical investigation subject administered a medicinal product and which does not necessarily have a causal relationship with this treatment. An AE can therefore be any unfavorable and unintended sign, symptom, or disease temporally associated with the use of a medicinal product, whether or not considered related to the medicinal product.

AEs also include the following:

- Pre- or post-treatment complications that occur as a result of protocol mandated procedure (e.g. such as venipuncture, biopsy) during or after Screening (before the administration of study investigational medicinal product).

- Any pre-existing condition that increases in severity, or changes in nature during or as a consequence of the study investigational medicinal product phase of a human clinical trial, will also be considered an AE.
- Complications and termination of pregnancy (see Section 8.2.2 for additional information)
- All AEs that occur from the study screening visit onwards and throughout the duration of the study, including the follow-up off study medication period should be recorded as an AE.

An AE does not include the following:

- Medical or surgical procedures (e.g., surgery, endoscopy, tooth extraction, transfusion) performed; the condition that leads to the procedure is an AE.
- Pre-existing diseases or conditions or laboratory abnormalities present or detected before the screening visit that do not worsen.
- If progression of underlying malignancy is clearly consistent with the suspected progression of the underlying cancer as defined by RECIST 1.1, or with clinical symptoms (clinical progression), it should not be reported as an AE/SAE. Similarly, hospitalization due exclusively to the progression of underlying malignancy should NOT be reported as an SAE.
- Situations where an untoward medical occurrence has not occurred (e.g., hospitalization for elective surgery, social and/or convenience admissions).
- Any medical condition or clinically significant laboratory abnormality with an onset date before the consent form is signed and not related to a protocol-associated procedure is not an AE. It is considered to be pre-existing and should be documented on the medical history CRF.
- Uncomplicated pregnancy.
- An induced elective abortion to terminate a pregnancy without medical reason.

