- "Lack of efficacy" or "failure of expected pharmacological action" per se will not be reported as an AE or SAE. However, the signs, symptoms, and/or clinical sequelae resulting from lack of efficacy may be reported as AE or SAE if they fulfill the definition of an AE or SAE.

Serious Adverse Event

If an event is not an AE per definition above, then it cannot be an SAE even if serious conditions are met (e.g., hospitalization for signs/symptoms of the disease under study, death due to progression of disease).

A **SAE** is defined as any untoward medical occurrence that, at any dose:

- Results in death
- Is life-threatening. The term 'life-threatening' in the definition of 'serious' refers to an event in which the patient was at risk of death at the time of the event. It does not refer to an event, which hypothetically might have caused death, if it were more severe.
- Requires inpatient hospitalization or prolongation of existing hospitalization. In general, hospitalization signifies that the patient has been detained (usually involving at least an overnight stay) at the hospital or emergency ward for observation and/or treatment that would not have been appropriate in the physician's office or outpatient setting. Complications that occur during hospitalization are AEs. If a complication prolongs hospitalization or fulfills any other serious criteria, the event is serious. When in doubt as to whether "hospitalization" occurred or was necessary, the AE should be considered serious. Hospitalization for elective treatment of a pre-existing condition that did not worsen from baseline is not considered an AE.
- Results in persistent disability/incapacity. The term disability means a substantial disruption of a person's ability to conduct normal life functions. This definition is not intended to include experiences of relatively minor medical significance such as uncomplicated headache, nausea, vomiting, diarrhea, influenza, and accidental trauma (e.g., sprained ankle) which may interfere with or prevent everyday life functions but do not constitute a substantial disruption.
- Is a congenital anomaly/birth defect in the offspring of a subject who received investigational medicinal product.

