- Other situations. Medical or scientific judgment should be exercised in deciding whether SAE reporting is appropriate in other situations such as important medical events that may not be immediately life-threatening or result in death or hospitalization but may jeopardize the patient or may require medical or surgical intervention to prevent one of the other outcomes listed in the above definition. These events should usually be considered serious. Examples of important medical events include invasive or malignant cancers, intensive treatment in an emergency room or at home for allergic bronchospasm, blood dyscrasias or convulsions that do not result in hospitalization, or development of drug dependency or drug abuse.

8.2.1.2. Time Period and Frequency for Collecting Adverse Event and Serious Adverse Event Information

All AEs and SAEs will be collected from the signing of the informed consent form (ICF) through the Follow-up visit.

Medical occurrences that begin before the start of study intervention but after obtaining informed consent will be recorded on the Medical History/Current Medical Conditions section of the CRF not the AE section.

Investigators are not obligated to actively seek AE or SAE after conclusion of the study participation. However, if the investigator learns of any SAE, including a death, at any time after a patient has been discharged from the study, and he/she considers the event to be reasonably related to the study intervention or study participation, the investigator must promptly notify the Sponsor.

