8.2.1.8. Follow-up of Adverse Events and Serious Adverse Events

The investigator is obligated to perform or arrange for the conduct of supplemental measurements and/or evaluations as medically indicated or as requested by CicloMed or its designee to elucidate the nature and/or causality of the AE or SAE as fully as possible. This may include additional laboratory tests or investigations, histopathological examinations, or consultation with other health care professionals.

If a patient dies during participation in the study or during a recognized follow-up period, the investigator will provide CicloMed or its designee with a copy of any post-mortem findings including histopathology.

New or updated information will be recorded in the originally completed CRF.

The investigator will submit any updated SAE data to the Sponsor within 24 hours of receipt of the information. Contacts for SAE reporting can be found in the Study Procedures Manual.

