9.5.3. Adverse Events

Clinical and laboratory AEs will be coded using the Medical Dictionary for Regulatory Activities (MedDRA). System Organ Class (SOC), High-Level Group Term (HLGT), High-Level Term (HLT), Preferred Term, and Lower-Level Term (LLT) will be attached to the clinical database.

AEs will be summarized on the basis of the date of onset for the event. A treatment-emergent AE will be defined as any AE that begins on or after the date of first dose of CPX-POM.

Summaries (number and percentage of patients) of treatment-emergent AEs (by SOC, and Preferred Term) will be provided by dose group and overall:

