9.5.4. Laboratory Evaluations

Summaries of clinical laboratory data will be provided using descriptive statistics. No inferential statistics will be provided. Quantitative values and change from baseline in quantitative values will be summarized by dose group. Listings of all laboratory results and reference ranges will be provided.

Graded laboratory abnormalities will be defined using the grading scheme based on CTCAE (4.03). The incidence of treatment-emergent laboratory abnormalities, defined as values that increase at least one toxicity grade from baseline at any time post baseline up to and including the date of last dose of study drug, will be summarized by treatment group. If baseline data are missing, then any graded abnormality (i.e., at least a Grade 1) will be considered treatment emergent.

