Sponsor: CicloMed
Protocol: CPX-POM-001
Statistical Analysis Plan
(TFL shells):
Version 1.0 / 02FEB2018

Table 14.3-1.1 - Overview of Adverse Events
 (Safety Population)

	CPX-POM 30 mg/m ² N=1 n (%)	CPX-POM [D2] mg/m ² N=X n (%)	CPX-POM [D3] mg/m ² N=X n (%)	CPX-POM [D4] mg/m ² N=X n (%)	CPX-POM [D5] mg/m ² N=X n (%)	CPX-POM [D6] mg/m ² N=X n (%)	CPX-POM [D7] mg/m ² N=X n (%)
Number of patients with at least one:							
AE	XX (XX.X)	XX (XX.X)	XX (XX.X)	XX (XX.X)	XX (XX.X)	XX (XX.X)	XX (XX.X)
TEAE *	XX (XX.X)	XX (XX.X)	XX (XX.X)	XX (XX.X)	XX (XX.X)	XX (XX.X)	XX (XX.X)
Related TEAE	XX (XX.X)	XX (XX.X)	XX (XX.X)	XX (XX.X)	XX (XX.X)	XX (XX.X)	XX (XX.X)
TEAE leading to discontinuation	XX (XX.X)	XX (XX.X)	XX (XX.X)	XX (XX.X)	XX (XX.X)	XX (XX.X)	XX (XX.X)
Related TEAE leading to discontinuation	XX (XX.X)	XX (XX.X)	XX (XX.X)	XX (XX.X)	XX (XX.X)	XX (XX.X)	XX (XX.X)
Serious TEAE	XX (XX.X)	XX (XX.X)	XX (XX.X)	XX (XX.X)	XX (XX.X)	XX (XX.X)	XX (XX.X)
Serious related TEAE	XX (XX.X)	XX (XX.X)	XX (XX.X)	XX (XX.X)	XX (XX.X)	XX (XX.X)	XX (XX.X)

* A treatment-emergent adverse events (TEAE) is defined as an adverse event which started on or after the first dose of CPX-POM administration.
 MedDRA version <version number>.

Program: (Program name.sas) (run on: DDMMYYYY HH:MM)

Filename: (Specify file name.rtf)

PROGRAMMING NOTES:

- "Leading to discontinuation" is derived from action taken = permanently discontinued.
- **A last column with the header 'CPX-POM All Doses' will also be displayed.**

Table 14.3-1.2 - Number (%) of Patients with Treatment-Emergent Adverse Events by System Organ Class and Preferred Term (Safety Population)

System Organ Class/ Preferred Term	CPX-POM 30 mg/m ² N=1 n (%)	CPX-POM [D2] mg/m ² N=X n (%)	CPX-POM [D3] mg/m ² N=X n (%)	CPX-POM [D4] mg/m ² N=X n (%)	CPX-POM [D5] mg/m ² N=X n (%)	CPX-POM [D6] mg/m ² N=X n (%)	CPX-POM [D7] mg/m ² N=X n (%)
Number of patients with at least one TEAE	XX (XX.X)	XX (XX.X)	XX (XX.X)	XX (XX.X)	XX (XX.X)	XX (XX.X)	XX (XX.X)
System Organ Class #1	XX (XX.X)	XX (XX.X)	XX (XX.X)	XX (XX.X)	XX (XX.X)	XX (XX.X)	XX (XX.X)
Preferred Term #1	XX (XX.X)	XX (XX.X)	XX (XX.X)	XX (XX.X)	XX (XX.X)	XX (XX.X)	XX (XX.X)
Preferred Term #2	XX (XX.X)	XX (XX.X)	XX (XX.X)	XX (XX.X)	XX (XX.X)	XX (XX.X)	XX (XX.X)
Preferred Term #3	XX (XX.X)	XX (XX.X)	XX (XX.X)	XX (XX.X)	XX (XX.X)	XX (XX.X)	XX (XX.X)
<etc>							
System Organ Class #2	XX (XX.X)	XX (XX.X)	XX (XX.X)	XX (XX.X)	XX (XX.X)	XX (XX.X)	XX (XX.X)

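### Events starting between consent and first dose have two conflicting recording rules, and the onset-only treatment-emergent definition can leave one that worsens on drug out of the treatment-emergent tables

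*Protocol*

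**What the plan says.** **Recording.** Protocol 8.2.1.1 includes among AEs "All AEs that occur from the study screening visit onwards and throughout the duration of the study", off-drug follow-up included. It names complications of protocol procedures before drug as AEs, and it treats a condition as pre-existing when its onset precedes signature of the consent form. Section 8.2.1.2 opens by collecting all AEs and SAEs from consent through the Follow-up visit. Its next paragraph reads "Medical occurrences that begin before the start of study intervention but after obtaining informed consent will be recorded on the Medical History/Current Medical Conditions section", and adds that the AE page is not to be used. Section 8.2.3.6 sends clinically significant laboratory abnormalities noted during Screening to medical history. Table 1 marks AE collection at Screening.

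**Treatment emergence.** Protocol 9.5.3 summarizes AEs by onset date and states "A treatment-emergent AE will be defined as any AE that begins on or after the date of first dose of CPX-POM". The footnote to SAP Table 14.3-1.1 agrees: a treatment-emergent event "is defined as an adverse event which started on or after the first dose of CPX-POM administration". Neither mentions worsening. On follow-up of AEs, Protocol 8.2.1.8 says "New or updated information will be recorded in the originally completed CRF". For laboratory abnormalities, by contrast, Protocol 9.5.4 counts "values that increase at least one toxicity grade from baseline at any time post baseline", up to the date of last dose.

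**The concern.** The period at issue is Screening, up to 28 days per patient. A site cannot obey both halves of 8.2.1.2 for an event that starts in it, and about six centers are planned, so mixed practice is foreseeable.

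Two things are at stake. First, the Medical History paragraph makes no exception for serious events or procedure complications, so it steers staff away from the page on which such events should be recorded and from which prompt reporting starts. Second, whether post-dose worsening of a screening-onset event counts as treatment-emergent can depend on which page the site used at onset, not on what happened to the patient. In a first-in-human trial with dose groups of one to six patients, the treatment-emergent tables are a principal safety output and one patient is visible in them.

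**Working it through.** No power, sample-size or event-rate figure is involved, and the plan states none to reproduce. The check sets the rules side by side and traces one event through them.

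**Step 1: which page?** For onset after consent and before first dose:

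- AE page: 8.2.1.1 (Screening onward; pre-dose procedure complications), 8.2.1.2 opening sentence (from consent), Table 1 (AEs marked at Screening).
- Medical history: 8.2.1.2 next paragraph (all such occurrences), 8.2.3.6 (clinically significant Screening laboratory findings).

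The two groups give opposite instructions for the same event.

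**Step 2: trace an illustrative event.** Fatigue, Grade 1 on Day -5 (after consent), rises to Grade 3 on Day 4.

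*Route A* follows the AE-page rule. The record opens with onset on Day -5. When the grade rises, 8.2.1.8 points to the existing record, and no text asks for a new record or a new onset date. Onset stays before first dose.

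*Route B* follows the Medical History rule. Nothing goes on the AE page at onset. The rise can then be reported as a new AE, because 8.2.1.1 counts a pre-existing condition that increases in severity as an AE. If dated at the rise, its onset is Day 4.

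| Output | Route A | Route B |
|---|---|---|
| Onset carried into analysis | Day -5 | Day 4 |
| Overall AE row, Table 14.3-1.1 | counted | counted |
| Treatment-emergent rows, Table 14.3-1.1 | not counted | counted where it qualifies |
| Tables 14.3-1.2 to 14.3-1.9 | not counted | counted where it qualifies |
| Listing 16.2.7-1 | listed, pre-dose start | listed, post-dose start |
| Grade 2 or higher AE summary (Protocol 9.5.1) | counted | counted |

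Listing 16.2.7-1 has one start date and one severity per event, so under Route A it shows a severe event that began before drug and not when it became severe. Any CTCAE rise from Grade 1 or above reaches at least Grade 2, so the 9.5.1 summary, which has no treatment-emergent restriction, would include the patient. No shell for that summary appears among the SAP tables supplied.

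**Step 3: an event that does not worsen.** Under the AE-page rule it is in the overall AE row and the listing; under the Medical History rule it is in neither. The overall AE row therefore also depends on site practice.

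**Step 4: size of one misplacement.** Change in a dose group's percentage = 100 × 1/n:

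- n = 1: 100 × 1/1 = 100 points
- n = 3: 100 × 1/3 = 33.3 points
- n = 6: 100 × 1/6 = 16.7 points

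This is only the weight of one patient. In the any-TEAE row it applies only if that patient has no other treatment-emergent event. The documents give no rate of screening-onset events, so no expected number can be derived.

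**The case against.** Much of the case for a milder reading stands.

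- **SAE reporting.** A reader might infer that 24-hour reporting falls away for a serious screening-procedure complication, because 8.2.1.1 says "If an event is not an AE per definition above, then it cannot be an SAE even if serious conditions are met". The documents do not support that. The bar turns on the AE definition, which expressly includes pre-dose procedure complications; the Medical History paragraph concerns the CRF page and does not amend the definition. Such an event remains an SAE, reportable within 24 hours under 8.2.1.4 and 8.2.1.5. What remains is a risk that it is filed in the wrong place.
- **Residual toxicity.** A reader might infer that worsening of Grade 1 toxicity left from prior therapy, which exclusion criterion 4 permits, is lost. With onset before consent it is medical history under 8.2.1.1, and its increase on drug is an AE that begins after first dose. The gap covers only onsets between consent and first dose.
- **Where the event survives.** It would be wrong to say that it appears only in the listing: the overall AE row and the 9.5.1 summary also hold it. Laboratory worsening has its own definition in 9.5.4 and its own grade tables.
- **The update sentence.** In 8.2.1.8 it follows text on supplemental evaluations and post-mortem findings. It does not mention grade increases or forbid a new entry, so a site could open a new record dated at the worsening. The omission is possible, not certain; but nothing instructs a site to avoid it.
- **Convention.** Onset-only treatment emergence is stated consistently in both documents. Consistency does not cure its interaction with two recording rules, or its difference from the protocol's own laboratory definition.

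**Conclusion.** The concern holds in two parts. The recording rules for consent to first dose contradict each other, within 8.2.1.2 and between 8.2.3.6 and 8.2.1.1. And because treatment emergence rests on onset alone, a screening-onset event recorded as an AE that worsens on drug can be left out of the treatment-emergent rows and tables, while the same event filed as history can be counted.

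The effect is on the completeness and comparability of the reported AE tables, and on the reliability of recording serious pre-dose events. A reader might extend it to dose escalation or the MTD. The DLT definition in 4.1 uses grade, duration and relatedness, not the treatment-emergent flag, so that rule is not directly affected.

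The conclusion assumes that updates are made on the original record with its original onset date, and that no unseen text settles the matter. The SAP supplied consists of table and listing shells, and the CRF instructions and Study Procedures Manual are not among the documents, so a fuller definition there cannot be excluded. The frequency of affected events is unknown. The point should be corrected, since the remedy is cheap and safety is the trial's main output.

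**What to change.** 1. **One recording rule.** Replace the Medical History paragraph in Protocol 8.2.1.2, and align 8.2.3.6, with 8.2.1.1: an event with onset after consent and before first dose goes on the AE page as a pre-treatment AE, including clinically significant new Screening laboratory findings. Medical history is kept for onset before consent. State that the existing 24-hour SAE reporting applies throughout this period, procedure complications included. Changing 8.2.1.2 alone would leave 8.2.3.6 in conflict.
2. **Treatment-emergent definition.** In Protocol 9.5.3 and the SAP Table 14.3-1.1 footnote, define a treatment-emergent AE as one that begins, or worsens in CTCAE grade, on or after first dose.
3. **Date of worsening.** In 8.2.1.8 and the CRF guidance, require the date of a post-dose grade increase to be captured, for example as a new record with its own onset date, so that the definition can be programmed.

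Cost: protocol, CRF-guidance and SAP-footnote wording, plus slightly more data entry when a grade changes. No assessment is added. Treatment-emergent counts may rise slightly.

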8.2.1.3. Method of Detecting Adverse Events and Serious Adverse Events

Care will be taken not to introduce bias when detecting AEs and/or SAEs. Open-ended and non-leading verbal questioning of the patient is the preferred method to inquire about AE occurrences.

8.2.1.4. Regulatory Reporting Requirements for Serious Adverse Events

Prompt notification (within 24 hours from the first time a site team member is made aware of the event) by the investigator to the Sponsor of a SAE is essential so that legal obligations and ethical responsibilities towards the safety of patients and the safety of a study intervention under clinical investigation are met.

The Sponsor has a legal responsibility to notify both the local regulatory authority and other regulatory agencies about the safety of a study intervention under clinical investigation. The Sponsor will comply with country-specific regulatory requirements relating to safety reporting to the regulatory authority, Institutional Review Boards (IRB), and investigators.

Investigator safety reports must be prepared for suspected unexpected serious adverse reactions (SUSAR) according to local regulatory requirements and Sponsor policy and forwarded to investigators as necessary.

An investigator who receives an investigator safety report describing a SAE or other specific safety information (e.g., summary or listing of SAEs) from the Sponsor will review and then file it along with the Investigator's Brochure and will notify the IRB, if appropriate according to local requirements.

8.2.1.5. Reporting Procedures

When an AE/SAE occurs, it is the responsibility of the investigator to review all documentation (e.g., hospital progress notes, laboratory reports, and diagnostics reports) related to the event. The investigator will then record all relevant AE/SAE information in the CRF.

It is not acceptable for the investigator to send photocopies of the patient's medical records in lieu of completion of the AE/SAE CRF page. There may be instances when copies of medical records for certain cases are requested by CicloMed or its designee. In this case, all

patient identifiers, with the exception of the patient number, will be redacted on the copies of the medical records before submission.

The investigator will attempt to establish a diagnosis of the event based on signs, symptoms, and/or other clinical information. Whenever possible, the diagnosis (not the individual signs/symptoms) will be documented as the AE/SAE.

All SAEs will be recorded and reported to the Sponsor or their designee within 24 hours from the time any site team member is made aware of the event. The investigator will submit any updated SAE data to the Sponsor within 24 hours of it being available. If any part of the source providing details of the event is not available, the Investigator will submit the SAE with as much information as he/she has at the time of the reporting requirements.

Contacts and procedures for SAE reporting can be found in the Study Procedures Manual.

8.2.1.6. Assessment of Causality

The investigator is obligated to assess the relationship between CPX-POM and each occurrence of each AE/SAE as follows:

- There is a "reasonable possibility" of a relationship between the CPX-POM and the AE. This conveys that there are facts, evidence, and/or arguments to suggest a causal relationship, rather than a relationship cannot be ruled out.
- There is not a "reasonable possibility" of a relationship between CPX-POM and the AE.

The investigator will use clinical judgment to determine the relationship. Alternative causes, such as underlying disease(s), concomitant therapy, and other risk factors, as well as the temporal relationship of the event to study intervention administration will be considered and investigated. The investigator will also consult the Investigator's Brochure (IB) in his/her assessment.

For each AE/SAE, the investigator must document in the medical notes that he/she has reviewed the AE/SAE and has provided an assessment of causality.

There may be situations in which an SAE has occurred and the investigator has minimal information to include in the initial report to the Sponsor or contract research organization (CRO). However, it is very important that the investigator always make an assessment of causality for every event before the initial transmission of the SAE data to the Sponsor or CRO. The investigator may change his/her opinion of causality in light of follow-up information and send a SAE follow-up report with the updated causality assessment.

The causality assessment is one of the criteria used when determining regulatory reporting requirements.

The relationship to study procedures (e.g., invasive procedures such as venipuncture or biopsy) should also be assessed using the following considerations:

- There is a reasonable possibility that the AE occurred as a result of protocol-mandated procedures such as venipuncture or biopsy.
- There is not a reasonable possibility that the AE occurred as a result of a protocol-mandated procedure.

